### 3. Study Design

As mentioned in section 2, this project consists of two distinct aims: aim 1 (usability) and aim 2 (RCT). Aim 1 of this project will be conducted within a population of 5 to 15 healthy volunteers using a single study visit lasting approximately 30 to 60 minutes in which they will be asked to provide feedback on the app and its contents. Individuals enrolled into this aim will be asked to provide feedback via written communication. Feedback will be used to improve the app for Aim 2 (RCT).

Aim 2, which is the main focus of this exploratory pilot randomized clinical trial (RCT) is to be conducted within a population of 60 cardio-respiratory survivors with a 3-month follow-up. Eligible patients will be those individuals who are admitted to the hospital and receive treatment for cardio or respiratory failure. Additional characteristics of the target population are those that exhibit high psychological distress, as defined by their scoring at the time of hospital discharge via the Hospital Anxiety and Depression Scale (HADS) and Post Traumatic Stress Scale (PTSS) surveys. Eligible patients will be identified via daily electronic medical record (EMR) review and approached for consent while still hospitalized. Patients will be

asked to complete app registration and baseline survey completion post-consent, but at the time of hospitalization, if possible. Upon discharge, patients will be asked to complete survey 1, T1, to assess their levels of psychological distress. Should the patient demonstrate high enough levels of psychological distress, they will be randomized to 1 of 3 treatment arms:

- Arm 1: mCST Intervention Group 1 (self-directed coping skills training app with CST therapist intro call)
- Arm 2: mCST Intervention Group 2 (self-directed coping skills training app only)
- Arm 3: usual care (control group; no CST therapist and no coping skills training app)

Each participant, regardless of randomization arm will be asked to complete the following surveys at the listed time points below:

- Baseline (during hospitalization, post consent)
  - Collect sociodemographic data and establish baseline psychological distress.
- T1 (at the time of hospital discharge, within 1 week of returning to home but no more than 1 month (30 days) from discharge)
  - Complete the HADS, PTSS, and PHQ-10, QOL 100-point visual analog scale, IADL/ADLs
- T2 (1 month (30 days) post date of discharge; up to 2 months (60 days) for completion)

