#### **5. Study Population**

Blueprint is centered around the RCT portion of this pilot study. As such, the primary characteristics of the targeted study population will be those individuals who have been admitted to a hospital environment and are seriously ill due to respiratory failure or insufficiency (i.e., conditions that typically require respiratory support such as pneumonia, acute respiratory distress syndrome [ARDS], influenza, trauma, and post-op complications) or cardiac failure or insufficiency (i.e., conditions that require advanced cardiac support such

as septic shock, myocardial infarction, cardiogenic shock, and congestive heart failure). Additionally, given the world-wide pandemic of 2020, patients who experience a hospital admission due to COVID-19 and require respiratory and/or cardiac support will also be enrolled.

**Eligibility Criteria:** Patients who are deemed eligible for study participation will ultimately be those individuals who experience high levels of psychological distress (i.e., HADS total  $\geq 8$ ).

Specifically, patients enrolled into this pilot, RCT will meet the following criteria:

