### Inclusion Criteria (at the time of hospital discharge; at home)

1. Elevated baseline psychological distress symptoms, defined as HADS total score of  $\geq 8$  at the completion of survey 1 (T1).

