- **Consented:** defined as any individual who is approached for consent and voluntarily chooses to consent to the study, the procedures, risks and benefits with the understanding that they may withdraw at any time. A signed/dated informed consent must be on record to account for this individual. Patients, enrolled in the aim 2, who reach this status will be required to complete T1 at the time of hospital discharge within 1 week but no more than 1 month from returning to home. Individuals who are assigned this status must be noted on the enrollment log.

- **Declined:** defined as any individual who was approached for consent, but opted to NOT consent and therefore to NOT participate in the study. Individuals who are assigned this status must be noted on the screening log.
- **Randomized (aim 2 only):** defined as any patient who was consented to the study, is discharged from hospital to home, completes T1 survey, and continues to meet all eligibility criteria (see Eligibility Criteria, section 5). Patients who reach this status will be required to interact with the app on a daily basis for 1 month and then complete T2 and T3. Patients who are assigned this status must be maintained on the enrollment log.
- **Screen Failed (aim 2 only):** defined as any patient who was consented to the study, is discharged from hospital to home, and completes T1 survey, and DOES NOT meet all eligibility criteria (see Eligibility Criteria, section 5). Patients who reach this status have no additional follow-ups or study requirements. Patients who are assigned this status must be maintained on the enrollment log.

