## Study Visits

For aim 1, each participant will be asked to complete a singular study visit that last approximately 30-60 minutes. During this study visit, post consent, the individual will be asked to do the following:

- Find and install the Pattern Health app
- Register to the Blueprint study
- Complete baseline survey
- Randomize to 1 of 3 arms or screen fail purposely
- Provide feedback on app content and usability.

For aim 2, each consented patient will be asked to complete up to four individual study visits.

- **Baseline:** this visit is to occur post-consent (same day, ideally) at the time of hospital admission just prior to discharge. However, this visit may occur at the time of hospital discharge within 1-3 days of returning to home. At this visit, the following will occur:
  - App Registration
  - Baseline Survey Completion
- **T1 (Day 0) (+30 days):** this visit is to occur at the time of hospital discharge to home, ideally within the first week (7 days) of returning to home; however, it can occur up to 1 month (30 days) from the time of hospital discharge to home. At this visit, the patient will complete the T1 survey via the app, which includes the HADS, PTSS, and PHQ-10 surveys. Score dependent, the patient will be randomized to 1 of 3 arms: Group 1 (Blueprint app), Group 2 (Blueprint app + therapist), and Group 3 (control; no Blueprint app and no therapist). If the patient's psychological distress score is too low; he/she will receive an automated alert via the app describing they are not eligible and their study participation is complete.
- **T2 (Day 30) (+60 days):** this visit is to occur post 1 month randomization for those patients who remain eligible to participate in the study. HADS, PTSS, and PHQ-10 surveys will be administered again. If the patient's survey scores indicate high levels of distress, as defined by a triggered SI alert or increased distress score from T1, a delegated study team member will contact the patient for safety precautions.

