97. I'm doing jobs or tasks automatically, without being aware of what I'm doing.

Response is **\*\*one\*\*** of:

- Almost always
- Very frequently
- Somewhat frequently
- Somewhat infrequently
- Very infrequently
- Almost never

98. I'm finding myself preoccupied with the future or the past.

Response is **\*\*one\*\*** of:

- Almost always
- Very frequently
- Somewhat frequently
- Somewhat infrequently
- Very infrequently
- Almost never

99. I'm finding myself doing things without paying attention.

Response is **\*\*one\*\*** of:

- Almost always
- Very frequently
- Somewhat frequently
- Somewhat infrequently
- Very infrequently
- Almost never

100. Click Next to submit your answers and see your results.

(This is a score screen that requires no response)

101. Thank you.

(This is an information screen that requires no response)

After reviewing your results you were found to have a low needs score, and this is a good thing! You are not required to complete any other surveys or exercises. Your participation has been completed as of today.

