2.1 Inclusion Criteria

Patients included in Blueprint satisfied the following inclusion criteria:

At time of hospital admission:

- Age ≥ 18 years
- Managed in an adult ICU, step-down unit, or specialized care unit for ≥ 24 hours during the time in which inclusion criterion #3 is met.
- Presence of acute cardiac or respiratory failure, defined as having ≥ 1 of the following:
 - Acute respiratory failure / insufficiency, defined as ≥ 1 of the following:
 - Mechanical ventilation via endotracheal tube for ≥ 4 hours
 - Non-invasive ventilation (CPAP, BiPAP) for ≥ 4 hours in a 24-hour period provided for acute respiratory failure in an ICU (not for obstructive sleep apnea or other stable use)
 - High flow / opti-flow nasal cannula or face mask oxygen use
 - $\geq 25\%$ increase in baseline nasal cannula rate
 - Acute cardiac failure / insufficiency, defined as ≥ 1 of the following:
 - use of vasopressors for shock of any etiology
 - use of inotropes for shock of any etiology
 - use of pulmonary vasodilators
 - use of aortic balloon pump or cardiac assist device for cardiogenic shock
 - use of diuretic intravenous drip
- Cognitive status intact, defined as:
 - No history of significant cognitive impairment (e.g., dementia)
 - Absence of current, significant cognitive impairment (≥ 3 errors on the Callahan cognitive status screen)
 - Decisional capacity present
- Absence of severe and/or persistent serious mental illness that could disrupt study participation, as noted in the electronic medical record (EMR) or affirmed by clinical staff at the time of screening and approach for consent. Defined as any of the following:

- Treatment for severe or unstable mental illness (e.g., psychosis, schizophrenia) within the last 6 months preceding the current hospital admission
- Active substance abuse that impairs ability to participate
- Endorsing suicidality at time of admission or informed consent discussion
- English fluency.

At time of discharge:

- Elevated baseline psychological distress symptoms, defined as HADS total score of ≥ 8 at the completion of survey 1, T1.

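### The T1 message that appears to end participation for screen failures is more reassuring than the HADS-only entry rule supports, and it points to no source of help

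*Protocol*

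**What the plan says.** Near the end of the T1 survey (Protocol, Appendix 3 G), item 100 is a score screen. Item 101 then says: "After reviewing your results you were found to have a low needs score, and this is a good thing". It adds that no more surveys or exercises are required and that participation is finished that day. Item 102 is the other ending and congratulates the patient on being enrolled.

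Protocol Section 7, Study Visits, describes what happens at T1 when the distress score is too low: "he/she will receive an automated alert via the app describing they are not eligible and their study participation is complete". Under the Screen Failed status in the same section, "Patients who reach this status have no additional follow-ups or study requirements".

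The entry rule appears in three places. Protocol Section 5 describes eligible patients as "individuals who experience high levels of psychological distress (i.e., HADS total" of 8 or more). The discharge inclusion criterion reads "Elevated baseline psychological distress symptoms, defined as HADS total score of" 8 or more at T1. SAP Section 2.1 repeats it: "Elevated baseline psychological distress symptoms, defined as HADS total score of ≥ 8 at the completion of survey 1, T1". Protocol Section 3, however, describes high distress at discharge as determined "via the Hospital Anxiety and Depression Scale (HADS) and Post Traumatic Stress Scale (PTSS) surveys", and gives no PTSS value.

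**The concern.** Falling below an entry threshold on one instrument means that the patient does not qualify for this study. It does not mean that the patient's needs are low. Item 101 turns the first statement into the second and adds that the result is good news. It does so straight after a survey that has asked about nightmares, guilt, fear of reminders of intensive care and other post-traumatic symptoms.

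A screen-failed patient has no further follow-up, so this is the last message the survey gives. Someone troubled mainly by post-traumatic symptoms could read it as an all-clear and be less inclined to use the contacts already provided. What is at stake is a small matter of patient safety and communication.

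**Working it through.** No sample size, power or error-rate figure is involved, so the check compares the texts.

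1. **Is item 101 the screen-fail ending?** The printed survey attaches no condition to it. Items 101 and 102 cannot both apply to one patient: one closes participation, the other opens the programme. Section 7 describes an automated closing alert for patients whose distress score is too low, and of the two endings only item 101 fits. The inference is well supported, but it remains an inference.

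2. **What decides eligibility?** The only number given is a HADS total of at least 8 (Protocol Section 5 and the discharge inclusion criterion; SAP Section 2.1). Section 3 names the PTSS alongside the HADS without a cut-off. Section 7 says that randomisation depends on score after listing HADS, PTSS and PHQ-10, again with no other cut-off. A needs score is not defined in either document.

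3. **What follows under the written rule?** The HADS is items 18 to 31 (14 items). The PTSS is items 42 to 51 (10 items, each rated 1 to 7), so its total can run from 10 × 1 = 10 to 10 × 7 = 70. A patient with a HADS total of 7 screen-fails whatever the PTSS total, because that total does not enter the rule. The message is the same for every such patient. The two scales overlap in content (tension and low mood, for example), so very high PTSS totals with HADS below 8 should be uncommon. The range shows only that the rule does not look at the PTSS, not how many patients are affected.

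4. **Does the screen match the alert in Section 7?** The alert has two parts: the patient is not eligible, and participation is complete. Item 101 gives the second and leaves out the first. This mismatch can be seen directly and needs no assumption about symptoms.

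5. **What help is already written, and does item 101 mention it?**
   - Investigator contact at all hours, shown in the consent form, of which each participant receives a copy (Section 12).
   - Study telephone number and email address (Section 12, General oversight).
   - An information sheet with mental health contact numbers for symptoms including PTSD, and a resource list for all subjects at the start of the programme (Section 12, oversight plans for severe distress).
   - A check-in call when a total symptom score is high, with no instrument, cut-off or time point stated (Section 12, Reporting Procedures).
   - Adverse-event assessment at T1, by record review and/or telephone (Appendix 1), with events recorded for 7 days (non-serious) or 30 days (serious) after the last day of participation (Section 12).

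   Item 101 mentions none of these.

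6. **How many patients?** The documents give no T1 screen-fail rate, no correlation between HADS and PTSS and no PTSS cut-off. No estimate is possible.

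**The case against.** The strongest objection is that the harm depends on things not printed. The app's branching is not shown, and neither is the content of the item 100 score screen. If the app also uses the PTSS, as Section 3 could be read to imply, or if item 100 shows scores or resources, the scenario shrinks or disappears. This stands, and it is why the point is conditional on the app following the written rule. It would not supply the missing statement of ineligibility.

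Second, screen-failed patients are consented participants, and the general safeguards are not limited to later visits. Section 12 expressly foresees mental health issues coming to light through survey responses. This also stands. A reader might infer that these patients are left without help; the documents do not support that.

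Third, the score-triggered contact at T2 and T3 ("survey scores indicate high levels of distress, as defined by a triggered SI alert or increased distress score from T1") relies partly on a change from T1, which cannot exist at T1. Its absence from the T1 visit is therefore partly structural. The printed T2 and T3 endings carry no resource line either. Both observations are fair, but those endings merely thank the patient and offer no verdict on the patient's state.

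Finally, much of this can be called a matter of tone, and the change would identify no patient with a high PTSS total. That is true and limits the gain. It does not justify keeping a phrase that claims more than the rule can show.

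**Conclusion.** The point holds as an inexpensive, optional improvement. By inference, item 101 is the below-threshold ending. Its description of low needs as good news goes further than a rule resting on the HADS total alone, and it omits the ineligibility statement described in Section 7. The false-reassurance scenario also assumes that the app applies the written HADS threshold and nothing else.

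The number affected is probably small and cannot be estimated. Two stronger readings are tempting and not supported. One is that the app misclassifies patients or that the trial needs a PTSS cut-off: the app logic is not printed, and nothing in the entry rule as written is breached. The other is that the results are compromised: the message goes to patients who are not randomised, so the randomised comparison and the outcomes are unaffected.

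**What to change.** Replace item 101 with neutral text saying three things: the score was below this study's entry threshold, the patient is not eligible to continue, and participation is complete as of today. Delete the phrases *low needs* and *a good thing*. Add one line directing anyone troubled by symptoms to the mental health information sheet described in Protocol Section 12 and to the study contact number. Do not rely only on the crisis numbers in the Suicidality Response Plan, which were written for a different purpose.

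The cost is one app text update and an IRB notice of the wording change. Many screened-out patients will see a line they do not need. No PTSS cut-off and no extra staff time are required.

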**CLICK NEXT TO SAVE YOUR RESULT**

102. Thank you!

(This is an information screen that requires no response)

Congratulations! You are now enrolled in the Blueprint program. You will find new tasks added to your home screen daily.

You can then review your daily tip and complete your coping skills practice.

**CLICK NEXT TO SAVE YOUR RESULT**

#### [H. T2 Survey](#)

# T2

Second Survey

1. In the past month, have you been treated for depression, anxiety, PTSD, or any other psychiatric condition?

Response is \*\*Yes\*\* or \*\*No\*\*.

2. In the past month, have you been treated for depression or depressed mood?

Response is \*\*Yes\*\* or \*\*No\*\*.

3. Were you treated with medication?

Response is \*\*Yes\*\* or \*\*No\*\*.

4. Were you treated by a psychiatrist, psychologist, or counselor?

Response is \*\*Yes\*\* or \*\*No\*\*.

5. In the past month, have you been treated for anxiety?

Response is \*\*Yes\*\* or \*\*No\*\*.

6. Were you treated with medication?

Response is \*\*Yes\*\* or \*\*No\*\*.

7. Were you treated by a psychiatrist, psychologist, or counselor?

Response is \*\*Yes\*\* or \*\*No\*\*.

8. In the past month, have you been treated for post-traumatic stress disorder (PTSD)?

Response is \*\*Yes\*\* or \*\*No\*\*.

9. Were you treated with medication?

Response is \*\*Yes\*\* or \*\*No\*\*.

10. Were you treated by a psychiatrist, psychologist, or counselor?

Response is \*\*Yes\*\* or \*\*No\*\*.

11. In the past month, have you been treated for chronic pain?

Response is \*\*Yes\*\* or \*\*No\*\*.

12. Were you treated with medication?

Response is \*\*Yes\*\* or \*\*No\*\*.

13. Were you treated by a psychiatrist, psychologist, or counselor?

Response is \*\*Yes\*\* or \*\*No\*\*.

14. Since you were last discharged from the hospital, have you been admitted to the hospital again?

Response is \*\*Yes\*\* or \*\*No\*\*.

15. How many times have you been admitted?

Response is \*\*one\*\* of:

- Once
- 2 times
- 3 or more times

16. For the next questions, select the option that best fits your current situation.

(This is an information screen that requires no response)

Click Next to continue.

17. I have someone to confide in or talk to about myself and my problems.

Response is \*\*one\*\* of:

- Never
- Rarely
- Sometimes
- Usually
- Always

18. At the end of an average month, what describes how you usually feel when you are paying the bills?

Response is \*\*one\*\* of:

- Short on money and need more to pay bills
- Barely have enough to pay bills and for basic needs
- Have enough for just a few extra things
- Completely comfortable

19. Please select the response that describes how you felt in the past week.

(This is an information screen that requires no response)

Click Next to continue

20. I feel tense or wound up

Response is \*\*one\*\* of:

- Not at all
- Time to time, occasionally
- A lot of the time
- Most of the time

21. I still enjoy the things I used to enjoy

Response is \*\*one\*\* of:

- Definitely as much
- Not quite so much
- Only a little
- Hardly at all

22. I get a frightened feeling like something awful is about to happen

Response is \*\*one\*\* of:

- Not at all
- A little, but it doesn't worry me
- Yes, but not too badly
- Very definitely and quite badly

23. I can laugh and see the funny side of things

Response is \*\*one\*\* of:

- As much as I always could
- Not quite so much now
- Definitely not so much now
- Not at all

24. Worrying thoughts go through my mind

Response is \*\*one\*\* of:

- Only occasionally
- From time to time but not too often
- A lot of the time
- A great deal of the time

25. I feel cheerful

Response is \*\*one\*\* of:

- Most of the time
- Sometimes
- Not often
- Not at all

26. I can sit at ease and feel relaxed

Response is \*\*one\*\* of:

- Definitely
- Usually
- Not often
- Not at all

27. I feel as if I am slowed down

Response is \*\*one\*\* of:

- Not at all
- Sometimes
- Very often
- Nearly all of the time

28. I get a sort of frightened feeling like butterflies in the stomach

Response is \*\*one\*\* of:

- Not at all
- Occasionally
- Quite often
- Very often

29. I have lost interest in my appearance

Response is \*\*one\*\* of:

- I take just as much care as ever
- I may not take quite as much care
- I don't take as much care as I should
- Definitely

30. I feel restless as if I have to be on the move

Response is \*\*one\*\* of:

- Not at all
- Not very much
- Quite a lot
- Very much indeed

31. I look forward with enjoyment to things

Response is \*\*one\*\* of:

- As much as I ever did
- A bit less than I used to
- Definitely less than I used to
- Hardly at all

32. I get sudden feelings of panic

Response is \*\*one\*\* of:

- Not at all

- Not very often
- Quite often
- Very often indeed

33. I can enjoy a good book or radio or TV program

Response is \*\*one\*\* of:

- Often
- Sometimes
- Not often
- Very seldom

34. Over the last week or so, how often have you been bothered by the following problems?

(This is an information screen that requires no response)

Click Next to continue.

35. Feeling nervous, anxious or on edge

Response is \*\*one\*\* of:

- Not at all
- A couple of days
- More than half the days
- Nearly every day

36. Not being able to stop or control worrying

Response is \*\*one\*\* of:

- Not at all
- A couple of days
- More than half the days
- Nearly every day

37. Worrying too much about different things

Response is \*\*one\*\* of:

- Not at all
- A couple of days
- More than half the days
- Nearly every day

38. Trouble relaxing

Response is \*\*one\*\* of:

- Not at all
- A couple of days
- More than half the days
- Nearly every day

39. Being so restless that it is hard to sit still

Response is \*\*one\*\* of:

- Not at all
- A couple of days
- More than half the days
- Nearly every day

40. Becoming easily annoyed or irritable

Response is \*\*one\*\* of:

- Not at all
- A couple of days
- More than half the days
- Nearly every day

41. Feeling afraid as if something awful might happen

Response is \*\*one\*\* of:

- Not at all
- A couple of days
- More than half the days
- Nearly every day

42. The last few questions asked how often you were bothered by the problems. Now, please share show how much distress the problem caused you:

Response is \*\*one position\*\* in this scale:

- 0 (No distress)
- 10
- 20
- 30
- 40
- 50
- 60
- 70
- 80
- 90
- 100 (Serious distress)

43. In the last week or so, how often have you experienced the following.

(This is an information screen that requires no response)

Click Next to continue.

44. I had sleep problems.

Response is \*\*one position\*\* in this scale:

- 1 (Never)
- 2
- 3
- 4
- 5
- 6
- 7 (Always)

45. I had nightmares.

Response is \*\*one position\*\* in this scale:

- 1 (Never)
- 2
- 3
- 4
- 5
- 6
- 7 (Always)

46. I had depression or felt dejected/downtrodden.

Response is \*\*one position\*\* in this scale:

- 1 (Never)
- 2
- 3
- 4
- 5
- 6
- 7 (Always)

47. I had jumpiness- I am easily frightened by sudden sounds or movements.

Response is \*\*one position\*\* in this scale:

- 1 (Never)
- 2
- 3
- 4
- 5

- 6
- 7 (Always)

48. I had the need to withdraw from others.

Response is \*\*one position\*\* in this scale:

- 1 (Never)
- 2
- 3
- 4
- 5
- 6
- 7 (Always)

49. I had irritability - I was easily agitated, annoyed or angered.

Response is \*\*one position\*\* in this scale:

- 1 (Never)
- 2
- 3
- 4
- 5
- 6
- 7 (Always)

50. I had frequent mood swings.

Response is \*\*one position\*\* in this scale:

- 1 (Never)
- 2
- 3
- 4
- 5
- 6
- 7 (Always)

51. I had a bad conscience, blamed myself, had guilty feelings.

Response is \*\*one position\*\* in this scale:

- 1 (Never)
- 2
- 3
- 4
- 5
- 6
- 7 (Always)

52. I had fear of places or situations that remind me of the Intensive Care Unit.

Response is \*\*one position\*\* in this scale:

- 1 (Never)
- 2
- 3
- 4
- 5
- 6
- 7 (Always)

53. I had muscular tension.

Response is \*\*one position\*\* in this scale:

- 1 (Never)
- 2
- 3
- 4
- 5
- 6
- 7 (Always)

54. The last few questions asked how often you were bothered by the problems. Now, please share how much distress the problem caused you:

Response is \*\*one position\*\* in this scale:

- 0 (No distress)
- 10
- 20
- 30
- 40
- 50
- 60
- 70
- 80
- 90
- 100 (Serious distress)

55. Over the last 2 weeks, how much have you been bothered by any of the following problems?

(This is an information screen that requires no response)

Click Next to continue.

56. Pain

Response is \*\*one\*\* of:

- Not bothered at all
- Bothered a little
- Bothered a lot

57. Difficulty concentrating

Response is \*\*one\*\* of:

- Not bothered at all
- Bothered a little
- Bothered a lot

58. Weakness

Response is \*\*one\*\* of:

- Not bothered at all
- Bothered a little
- Bothered a lot

59. Feeling your heart pound or race

Response is \*\*one\*\* of:

- Not bothered at all
- Bothered a little
- Bothered a lot

60. Shortness of breath (or other breathing problems)

Response is \*\*one\*\* of:

- Not bothered at all
- Bothered a little
- Bothered a lot

61. Stiffness in joints or muscles

Response is \*\*one\*\* of:

- Not bothered at all
- Bothered a little
- Bothered a lot

62. Constipation or diarrhea

Response is \*\*one\*\* of:

- Not bothered at all
- Bothered a little
- Bothered a lot

63. Nausea, gas, or indigestion

Response is \*\*one\*\* of:

- Not bothered at all
- Bothered a little
- Bothered a lot

64. The last few questions asked how often you were bothered by the problems. Now, please share how much distress the problem caused you:

Response is \*\*one position\*\* in this scale:

- 0 (No distress)
- 10
- 20
- 30
- 40
- 50
- 60
- 70
- 80
- 90
- 100 (Serious distress)

65. In general, how would you rate your current quality of life?

Response is \*\*one position\*\* in this scale:

- 0 (Worst imaginable quality of life)
- 10
- 20
- 30
- 40
- 50
- 60
- 70
- 80
- 90
- 100 (Best imaginable quality of life)

66. Currently I am able to:

(This is an information screen that requires no response)

Click Next to continue.

67. ... bathe myself em>(either a sponge bath, tub bath, or shower)

Response is \*\*one\*\* of:

- Need no help
- Need some help or unable to do

68. ... dress myself em>(like putting on a shirt, buttoning and zipping, etc.)

Response is \*\*one\*\* of:

- Need no help
- Need some help or unable to do

69. ... feed myselfem> (holding fork, cutting food, drinking from a glass)

Response is \*\*one\*\* of:

- Need no help
- Need some help or unable to do

70. ... get from a bed to a chair by myself

Response is \*\*one\*\* of:

- Need no help
- Need some help or unable to do

71. ... control my bladder or bowels

Response is \*\*one\*\* of:

- Need no help
- Need some help or unable to do

72. ... use the toilet by myself

Response is \*\*one\*\* of:

- Need no help
- Need some help or unable to do

73. ... use the telephone em>(including looking up numbers and dialing)

Response is \*\*one\*\* of:

- Need no help
- Need some help or unable to do

74. ... get to places beyond walking distance em>(drive own car or travel alone in buses or taxis)

Response is \*\*one\*\* of:

- Need no help
- Need some help or unable to do

75. ... go shopping for groceries or clothes

Response is \*\*one\*\* of:

- Need no help
- Need some help or unable to do

76. ... prepare my own meals

Response is \*\*one\*\* of:

- Need no help
- Need some help or unable to do

77. ... do housework em>(wash dishes, clean floors, etc.)

Response is \*\*one\*\* of:

- Need no help
- Need some help or unable to do

78. ... take my own medicine

Response is \*\*one\*\* of:

- Need no help
- Need some help or unable to do

79. ... handle my own money em>(write checks, pay bills)

Response is \*\*one\*\* of:

- Need no help
- Need some help or unable to do

80. How much do you agree or disagree with each statement?

(This is an information screen that requires no response)

Click Next to continue.

81. I never give up.

Response is \*\*one\*\* of:

- Totally disagree
- Disagree somewhat
- Neutral
- Agree somewhat
- Totally agree

82. I do everything to get well.

Response is \*\*one\*\* of:

- Totally disagree
- Disagree somewhat
- Neutral
- Agree somewhat
- Totally agree

83. I keep fighting to get better.

Response is \*\*one\*\* of:

- Totally disagree
- Disagree somewhat
- Neutral
- Agree somewhat
- Totally agree

84. I am afraid of pain.

Response is \*\*one\*\* of:

- Totally disagree
- Disagree somewhat
- Neutral
- Agree somewhat
- Totally agree

85. I can hardly tolerate pain.

Response is \*\*one\*\* of:

- Totally disagree
- Disagree somewhat
- Neutral
- Agree somewhat
- Totally agree

86. I am tough to myself when in pain.

Response is \*\*one\*\* of:

- Totally disagree
- Disagree somewhat
- Neutral
- Agree somewhat
- Totally agree

87. I view my illness as a personal learning experience.

Response is \*\*one\*\* of:

- Totally disagree
- Disagree somewhat
- Neutral
- Agree somewhat
- Totally agree

88. I am able to turn my illness into something positive.

Response is \*\*one\*\* of:

- Totally disagree
- Disagree somewhat
- Neutral
- Agree somewhat
- Totally agree

89. I use my illness in a creative way.

Response is \*\*one\*\* of:

- Totally disagree
- Disagree somewhat
- Neutral
- Agree somewhat
- Totally agree

90. I am gloomy about recovery.

Response is \*\*one\*\* of:

- Totally disagree
- Disagree somewhat
- Neutral
- Agree somewhat
- Totally agree

91. I feel the future is bleak.

Response is \*\*one\*\* of:

- Totally disagree
- Disagree somewhat
- Neutral
- Agree somewhat
- Totally agree

92. I do not believe in a happy ending.

Response is \*\*one\*\* of:

- Totally disagree
- Disagree somewhat
- Neutral
- Agree somewhat
- Totally agree

93. I resign myself to my destiny.

Response is \*\*one\*\* of:

- Totally disagree
- Disagree somewhat
- Neutral
- Agree somewhat
- Totally agree

94. I reconcile myself to the inevitable.

Response is \*\*one\*\* of:

- Totally disagree
- Disagree somewhat
- Neutral
- Agree somewhat
- Totally agree

95. I accept whatever will happen.

Response is \*\*one\*\* of:

- Totally disagree
- Disagree somewhat
- Neutral
- Agree somewhat
- Totally agree

96. Please indicate how frequently or infrequently you've been having each experience over the past 3 days, including today.

(This is an information screen that requires no response)

Click Next to continue.

97. I'm finding it difficult to stay focused on what's happening in the present.

Response is \*\*one\*\* of:

- Almost always
- Very frequently
- Somewhat frequently
- Somewhat infrequently
- Very infrequently
- Almost never

98. I'm rushing through activities without being really attentive to them.

Response is \*\*one\*\* of:

- Almost Always
- Very frequently
- Somewhat frequently
- Somewhat infrequently
- Very infrequently
- Almost never

99. I'm doing jobs or tasks automatically, without being aware of what I'm doing.

Response is \*\*one\*\* of:

- Almost always
- Very frequently
- Somewhat frequently
- Somewhat infrequently
- Very infrequently
- Almost never

100. I'm finding myself preoccupied with the future or the past.

Response is \*\*one\*\* of:

- Almost always
- Very frequently
- Somewhat frequently
- Somewhat infrequently
- Very infrequently
- Almost never

101. I'm finding myself doing things without paying attention.

Response is \*\*one\*\* of:

- Almost always
- Very frequently
- Somewhat frequently
- Somewhat infrequently
- Very infrequently
- Almost never

102. Please help us improve the Blueprint program by answering some questions about it. We are interested in your honest opinion, whether positive or negative.

(This is an information screen that requires no response)

Click Next to continue.

103. How would you rate the quality of the Blueprint program?

Response is \*\*one\*\* of:

- Excellent
- Good
- Fair
- Poor

104. Did you get the kind of program that you wanted?

Response is \*\*one\*\* of:

- Yes, definitely
- Yes, generally
- No, not really
- No, definitely not

105. To what extent has the Blueprint program met your needs?

Response is \*\*one\*\* of:

- Almost all of my needs have been met
- Most of my needs have been met
- Only a few of my needs have been met
- None of my needs have been met

106. If a friend were in need of similar help, would you recommend the Blueprint program to him or her?

Response is \*\*one\*\* of:

- Yes, generally

- Yes, generally
- No, not really
- No, definitely not

107. How satisfied are you with the amount of help you received in the Blueprint program?

Response is **\*\*one\*\*** of:

- Very satisfied
- Mostly satisfied
- Indifferent or mildly dissatisfied
- Quite dissatisfied

108. Has the Blueprint program helped you to deal more effectively with your problems or stresses?

Response is **\*\*one\*\*** of:

- Yes, it helped a great deal
- Yes, it helped somewhat
- No, it really didn't help
- No, it seemed to make things worse

109. In an overall, general sense, how satisfied are you with the Blueprint program?

Response is **\*\*one\*\*** of:

- Very satisfied
- Mostly satisfied
- Indifferent or mildly dissatisfied
- Quite dissatisfied

110. If you were to decide about participating or not in the Blueprint program, would you do it again?

Response is **\*\*one\*\*** of:

- Yes, definitely
- Yes, I think so
- No, I don't think so
- No, definitely not

111. Could you provide any comments about specific ways the Blueprint program helped or didn't help you?

Response is **\*\*free-form text\*\***.

112. Click Next to submit your answers and see your results.

(This is a score screen that requires no response)

113. Thank You!

(This is an information screen that requires no response)

Please click Next to exit the survey.

I. T3 Survey

T3

Third Survey

1. During the past month, have you been treated for depression, anxiety, PTSD, or any other psychiatric condition?

Response is \*\*Yes\*\* or \*\*No\*\*.

2. In the past month, have you been treated for depression or depressed mood?

Response is \*\*Yes\*\* or \*\*No\*\*.

3. Were you treated with medication?

Response is \*\*Yes\*\* or \*\*No\*\*.

4. Were you treated by a psychiatrist, psychologist, or counselor?

Response is \*\*Yes\*\* or \*\*No\*\*.

5. In the past month, have you been treated for anxiety?

Response is \*\*Yes\*\* or \*\*No\*\*.

6. Were you treated with medication?

Response is \*\*Yes\*\* or \*\*No\*\*.

7. Were you treated by a psychiatrist, psychologist, or counselor?

Response is \*\*Yes\*\* or \*\*No\*\*.

8. In the past month, have you been treated for post-traumatic stress disorder (PTSD)?

Response is \*\*Yes\*\* or \*\*No\*\*.

9. Were you treated with medication?

Response is \*\*Yes\*\* or \*\*No\*\*.

10. Were you treated by a psychiatrist, psychologist, or counselor?

Response is \*\*Yes\*\* or \*\*No\*\*.

11. In the past month, have you been treated for chronic pain?

Response is \*\*Yes\*\* or \*\*No\*\*.

12. Were you treated with medication?

Response is \*\*Yes\*\* or \*\*No\*\*.

13. Were you treated by a psychiatrist, psychologist, or counselor?

Response is \*\*Yes\*\* or \*\*No\*\*.

14. Since you were last discharged from the hospital, have you been admitted to the hospital again?

Response is \*\*Yes\*\* or \*\*No\*\*.

15. How many times have you been admitted?

Response is \*\*one\*\* of:

- Once
- 2 times
- 3 or more times

16. For the next questions, select the option that best fits your current situation.

(This is an information screen that requires no response)

Click Next to continue.

17. I have someone to confide in or talk to about myself and my problems.

Response is \*\*one\*\* of:

- Never
- Rarely
- Sometimes
- Usually
- Always

18. At the end of an average month, what describes how you usually feel when you are paying the bills?

Response is \*\*one\*\* of:

- Short on money and need more to pay bills
- Barely have enough to pay bills and for basic needs
- Have enough for just a few extra things

- Completely comfortable

19. Please select the response that describes how you felt in the past week.

(This is an information screen that requires no response)

